## 6. Data and Safety Monitoring

Phase 1 & 2: This study is minimal risk. The PI and co-investigators will monitor for adverse events and report any events according to RBHS IRB guidelines.

## Promoting Follow-Up Care Self-Management for Adolescent and Young Adult (AYA) Childhood Cancer Survivors

[name], MPH

Phase 3A & 3B: This study is minimal risk. The PI will convene a Data and Safety Monitoring Board (DSMB) composed of the biostatistician and a behavioral scientist and clinician who are not associated with the study. The committee will be responsible for oversight of patient safety and will meet yearly to review patient safety and trial progress. This review will include for each arm of the study: the number of patients enrolled, withdrawals, serious adverse events both expected and unexpected, and responses observed. All unexpected and/or serious adverse events (AEs) occurring during the active portion of the intervention or up to 30 days after the last peer mentor call, will be reported to the Rutgers Cancer Institute of New Jersey Office of Human Research Services and the Rutgers Biomedical Sciences Institutional Review Board (IRB) in accordance with IRB policy. The PI and study staff will continuously monitor for any potential AEs. Peer mentors will be instructed in how to assess and report adverse events during the mentor training and study staff will explicitly ask about adverse events during regular supervision sessions with each mentor. The research team will review and discuss via a teleconference any serious adverse events to ensure protections to the participants and security of the data, and discuss any modifications needed. If modifications are needed, they will be implemented immediately following standard IRB procedures. The Rutgers Cancer Institute of New Jersey Scientific Review Board and the IRB will review this Data and Safety Monitoring Plan and the study protocol prior to initiation of the study. A report with recommendations from the DSMB will be submitted annually to the IRB with the continuing review for the study.

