**Phase 3B: Usual Care Comparison.** The Usual Care group will complete surveys only. To select an appropriate comparison, we reviewed the literature of advantages/disadvantages of different designs. This study can be characterized as a phase IIb feasibility pilot focused on feasibility and acceptability, as well as detecting a clinically significant signal over noise. A usual care comparison group is recommended for initial evaluations of such interventions, as it maximizes statistical power and protects against falsely concluding that the intervention lacks efficacy. We will offer access to the online educational modules upon completion of all study procedures to the interested subjects in the usual care comparison group.

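### In Phase 3B the adverse-event reporting period and the only explicit adverse-event questioning exist in the intervention arm alone, so the serious-event counts the DSMB reviews by arm would not be comparable

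*Combined protocol and SAP*

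**What the plan says.** Section 6 (Data and Safety Monitoring, Phase 3A & 3B) sets the period for reporting unexpected or serious adverse events to the research office and the IRB. Events count if they occur while the intervention is active or "up to 30 days after the last peer mentor call".

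The same section describes three ways in which events come to light:
- Training: "Peer mentors will be instructed in how to assess and report adverse events during the mentor training".
- Supervision: "study staff will explicitly ask about adverse events during regular supervision sessions with each mentor".
- General monitoring: "The PI and study staff will continuously monitor for any potential AEs". This sentence is not limited to one arm, and it gives no contact, question or schedule.

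On oversight, the section says of the yearly DSMB meeting: "This review will include for each arm of the study: the number of patients enrolled, withdrawals, serious adverse events both expected and unexpected". No period is attached to that review.

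For the comparison arm, Section 4.1 (Phase 3B: Usual Care Comparison) says: "The Usual Care group will complete surveys only". Neither the Phase 3B measures table in Section 4.2 nor the survey content described in Section 4.3 lists an adverse-event item.

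**The concern.** A by-arm review of serious events is informative only if both arms are observed over the same period and asked in the same way. Here the start and end of the reporting period are intervention milestones, and the explicit questioning passes through a person whom usual-care participants do not have.

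An excess of events in the intervention arm could then reflect closer watching rather than harm. A true excess in usual care could equally be hidden. The DSMB would have no means of telling these apart from the counts it is given. The anchor also fails for an intervention participant who never has a mentor call, because the 30 days then have no starting point.

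**Working it through.** The plan states no figure to reproduce here. The check sets the provisions side by side, with one piece of arithmetic on the window.

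**Comparison of the arms**

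| Element | Intervention | Usual care |
|---|---|---|
| Start and end of reporting period (Section 6) | Active intervention, plus 30 days after last mentor call | Neither marker exists |
| Explicit questioning (Section 6) | Staff ask the mentor at supervision | None described |
| Frequency of questioning | Supervision is weekly once mentees are assigned (Section 4.1, Peer Mentor Training) | None described |
| General staff monitoring (Section 6) | Yes, method not stated | Yes, method not stated |
| Surveys (Section 3.1): baseline, ~8 weeks, ~5 months, ~12 months | Yes, no adverse-event item listed | Yes, no adverse-event item listed |
| Medical record release at last follow-up (Section 4.2) | Yes, to check healthcare use | Yes, to check healthcare use |
| Serious events reviewed by DSMB (Section 6) | Yes, no period stated | Yes, no period stated |

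The last four rows are common to both arms. The first three apply to one arm only, and they contain every specific adverse-event procedure in the plan.

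**Length of the intervention-arm window**

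- Inputs: intervention of about 8 weeks (Section 3.1) and a 30-day tail (Section 6). I assume the last mentor call falls at about week 8.
- Window = 8 × 7 + 30 = 86 days from baseline.
- As a share of the ~12-month follow-up: 86 / 365 = 0.236, about 24%.
- Usual-care window: cannot be calculated.

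The 86 days is a reporting window. Explicit questioning covers about 8 weeks of it, because supervision reviews the mentoring calls and no contact with the participant is described for the 30-day tail. The questioning is also indirect: staff ask the mentor, and no adverse-event question to the participant is described in either arm.

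**Illustration of what unequal ascertainment could do**

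The documents give no event risk, no detection rates and no allocation ratio, so the inputs below are assumptions: 25 per arm (half of 50), the same true risk in both arms, and 90% detection in the intervention arm.

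Expected recorded events = 25 × risk × detection.

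| True risk, both arms | Intervention, 90% detected | Usual care, 90% | Usual care, 50% | Usual care, 20% | Usual care, 0% |
|---|---|---|---|---|---|
| 5% | 1.125 | 1.125 | 0.625 | 0.25 | 0 |
| 10% | 2.25 | 2.25 | 1.25 | 0.5 | 0 |
| 20% | 4.5 | 4.5 | 2.5 | 1.0 | 0 |

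At a 10% risk, the expected gap from ascertainment alone runs from 0 events (equal detection) to 2.25 (no detection in usual care). The table shows how the gap depends on detection; it does not estimate the gap in this trial.

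**The case against.** The strongest reply is that Section 6 has staff monitoring continuously in both arms, that the study is minimal risk, and that tying institutional reporting to exposure is a defensible choice in a 50-person feasibility pilot. The Phase 3B analysis plan in Section 5 includes no safety comparison, and Section 6 gives no stopping rule, so no stated decision depends on by-arm event rates. The DSMB's by-arm list names serious events, which depend less on being asked about than minor ones.

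All of this limits the consequence. It does not make the counts comparable, because the general monitoring sentence names nothing that would reach a usual-care participant.

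A reader might infer more than the documents support:

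- *That usual-care events cannot be recorded, giving some number against zero.* Zero is right only for mentor-reported events. Staff monitoring may bring in others, so total capture in usual care is unspecified.
- *That the DSMB table is cut off at the 30-day window.* That window governs reporting to the research office and the IRB. The DSMB review has no stated period, so the defect there is the lack of a common period.
- *That intervention participants are actively questioned for the whole 86 days, about 12 weeks.* The 30-day tail has no described contact.
- *That distress in usual care would go unseen.* Fear of recurrence, stigma and shame, and managing emotions are surveyed in both arms at baseline, ~8 weeks and ~5 months. Withdrawals are reviewed by arm, reasons for drop-out are examined, and the requested records include sick visits. None of these is set up as adverse-event collection, but together they rule out that claim.

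**Conclusion.** The concern holds in a limited form. The Phase 3B reporting period is undefined for usual care, the only explicit questioning runs through mentors, and the DSMB is to look at serious events by arm without a common period. Ascertainment is more intensive in the intervention arm, so by-arm serious-event counts would not be comparable.

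The size of the difference cannot be computed from the documents. The practical impact is modest, and this is a worthwhile, cheap improvement rather than a flaw that threatens the trial's conclusions. The verdict assumes that the surveys contain no adverse-event item beyond what Sections 4.2 and 4.3 list, and that no separate procedure specifies how staff monitor usual care.

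**What to change.** 1. In Section 6, define one adverse-event period for both arms, counted from randomisation. One option is the length of the intervention period plus 30 days, about 86 days. State that the same period applies to the DSMB's by-arm counts.
2. Add the same brief adverse-event question, with date of onset, to the existing ~8-week and later surveys in both arms. The ~8-week survey falls at about day 56, before day 86, so the ~5-month survey is needed to cover the rest of the period, and dates are needed to place events inside it.
3. Show the DSMB the survey-solicited events by arm, with the number of surveys returned in each arm as the denominator. List mentor-reported events separately, since they can arise in one arm only.
4. Say in a sentence how general staff monitoring reaches usual-care participants.

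The cost is one extra survey item, a wording change and a few more reports to process. No new visit or contact is needed.

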## 7. Reporting Results

### 7.1 Individual Results

N/A

### 7.2 Aggregate Results

Aggregate results will be reported in scientific publications. Plain language summaries will also be made available at the end of the study. After participants complete the final assessment, we will have a separate form that they can voluntarily complete with preferred contact information (i.e., mail, email) to receive a summary of aggregate results. This information will be stored confidentially until the summary is provided, at which time the contact information will be destroyed.

### 7.3 Professional Reporting

It is expected that the results of this research will be submitted for publication in a timely manner following the conclusion of the study. The PI and all co-authors must review any abstract or manuscript prior to submission.

